Appendix 4 Proposed Summary Tables and Data Listings

Proposed Summary Tables:

- CT-1.1.1 Subject Disposition by Phase
- CT-1.1.2 Subject Disposition in Double-Blind Randomized Withdrawal Phase (Randomized Sample)
- CT-1.2.1 Subject Enrollment by Region, Country and Center
- CT-1.2.1 Subject Enrollment by Region, Country and Center (Randomized Sample)
- CT-1.3.1 Subject Enrollment by Age Group at Enrollment
- CT-1.3.2 Subject Enrollment by Age Group at Enrollment (Randomized Sample)
- CT-2.1 Reasons for Discontinuation by Phase (Enrolled Sample)
- CT-2.2 Reasons for Discontinuation (Randomized Sample)
- CT-3.1.1 Demographic Characteristics (Enrolled Sample)
- CT-3.1.2 Demographic Characteristics (Randomized Sample)
- CT-3.2.1 Baseline Disease Characteristics (Enrolled Sample)
- CT-3.2.2 Baseline Disease Characteristics (Randomized Sample)
- CT-4.1 Concomitant Medications: Medications Taken by Phase (Open-Label Safety Sample)
- CT-4.2.1 Concomitant Medications: Medications Taken Prior to Start of Study Therapy (Randomized Safety Sample)
- CT-4.2.2 Concomitant Medications: Medications Taken During Open-Label Stabilization Phase (Randomized Safety Sample)
- CT-4.2.3 Concomitant Medications: Medications Taken During Double-Blind Randomized Withdrawal Phase (Randomized Safety Sample)
- CT-4.2.4 Concomitant Medications: Medications Taken Post Study Therapy Period (Randomized Safety Sample)
- CT-5.1 Descriptive statistics for Relapse Rate (ITT Sample)
- CT-5.2.1 Yale Global Tic Severity Scale - Total Tic Score (YGTSS - TTS) - Mean Change from Baseline by Week - OC (Open-Label Efficacy Sample)
- CT-5.2.2 Yale Global Tic Severity Scale - Total Tic Score (YGTSS - TTS) - Mean Change from Baseline by Week - OC (ITT Sample)
- CT-5.3.1 Total Yale Global Tic Severity Scale Score - Mean Change from Baseline by Week - OC (Open-Label Efficacy Sample)
- CT-5.3.2 Total Yale Global Tic Severity Scale Score - Mean Change from Baseline by Week - OC (ITT Sample)
- CT-5.4.1 Clinical Global Impressions Scale for Tourette's Syndrome (CGI-TS) Severity score - Mean Change from Baseline by Week - OC (Open-Label Efficacy Sample)
- CT-5.4.2 Clinical Global Impressions Scale for Tourette's Syndrome (CGI-TS) Severity score - Mean Change from Baseline by Week - OC (ITT Sample)
- CT-5.5.1 Clinical Global Impressions Scale for Tourette's Syndrome (CGI-TS) Improvement Score - Mean by Week - OC (Open-Label Efficacy Sample)
- CT-5.5.2 Clinical Global Impressions Scale for Tourette's Syndrome (CGI-TS) Improvement Score - Mean by Week - OC (ITT Sample)
- CT-6.1.1 Simpson-Angus Scale Total Score - Mean Change from Baseline by Week - OC (Randomized Safety Sample)
- CT-6.1.2 Barnes Akathisia Rating Scale Global Score - Mean Change from Baseline by Week - OC (Randomized Safety Sample)
- CT-6.1.3 AIMS Movement Rating Score - Mean Change from Baseline by Week - OC (Randomized Safety Sample)
- CT-6.2.1 Columbia-Suicide Severity Rating Scale (C-SSRS) (children's version) - Suicidality (Randomized Safety Sample)
- CT-6.2.2 Columbia-Suicide Severity Rating Scale (C-SSRS) (children's version) by Type (Randomized Safety Sample)
- CT-7 Extent of Exposure to Investigational Medicinal Products Double-Blind Randomized Withdrawal Phase (Randomized Safety Sample)
- CT-8.1 Adverse Events (All Causalities) (Randomized Safety Sample)

- CT-8.2.1 Incidence of Treatment-Emergent Adverse Events by System Organ Class and MedDRA Preferred Term (Randomized Safety Sample)
- CT-8.2.2 Incidence of Treatment-Emergent Adverse Events by System Organ Class, MedDRA Preferred Term and Severity (Randomized Safety Sample)
- CT-8.2.3 Incidence and Occurrence (Number of Events) of non-Serious Treatment-emergent Adverse by System Organ Class and MedDRA Preferred Term (Randomized Safety Sample)
- CT-8.3.1 Incidence and Occurrence (Number of Events) of Potentially Drug-Related Treatment-Emergent Adverse Events by System Organ Class and MedDRA Preferred (Randomized Safety Sample)
- CT-8.3.2 Incidence of Potentially Drug-related Treatment-emergent Adverse Events by System Organ Class and MedDRA Preferred Term and Severity (Randomized Safety Sample)
- CT-8.4 Incidence of Deaths Due to Treatment-Emergent Adverse Events by System Organ Class and MedDRA Preferred Term (Randomized Safety Sample)
- CT-8.5.1 Incidence and Occurrence (Number of Events) of Serious Treatment-Emergent Adverse Events by System Organ Class and MedDRA Preferred Term (Randomized Safety Sample)
- CT-8.5.2 Incidence of Serious Treatment-emergent Adverse Events by System Organ Class and MedDRA Preferred Term and Severity (Randomized Safety Sample)
- CT-8.6.1 Incidence of Treatment-Emergent Adverse Events Resulting in Discontinuation from Trial by System Organ Class and MedDRA Preferred Term (Randomized Safety Sample)
- CT-8.6.2 Incidence of Treatment-Emergent Adverse Events Resulting in Discontinuation from Trial by System Organ Class, MedDRA Preferred Term and Severity (Randomized Safety Sample)
- CT-9.1 Listing of Deaths (Safety Sample)
- CT-9.2 Listing of Serious Adverse Events (Safety Sample)
- CT-9.3 Listing of Discontinuations of Study Medication Due to Adverse Events(Safety Sample)
- CT-10.1.1 Laboratory Test Results for Serum Chemistry - Mean Change from Baseline (Randomized Safety Sample)
- CT-10.1.2 Laboratory Test Results for Hematology - Mean Change from Baseline (Randomized Safety Sample)
- CT-10.1.3 Laboratory Test Results for Urinalysis - Mean Change from Baseline (Randomized Safety Sample)
- CT-10.1.4 Laboratory Test Results for Other Clinical Laboratory Tests - Mean Change from Baseline (Randomized Safety Sample)
- CT-10.2 Incidence of Laboratory Values of Potential Clinical Relevance (Randomized Safety Sample)
- CT-10.3.1 Listing of Laboratory Values of Potentially Clinical Relevance by Subject(Safety Sample)
- CT-10.3.2 Listing of Laboratory Values of Potentially Clinical Relevance by Type (Safety Sample)
- CT-10.3.3 Criteria for Laboratory Values of Potentially Clinical Relevance
- CT-10.4 Listing of Potentially Liver Injury Related Laboratory Test Abnormalities by Subject (Safety Sample)
- CT-11.1.1 Vital Sign Parameters - Mean Change from Baseline (Randomized Safety Sample)
- CT-11.1.2 Mean Change from Baseline in Weight, Height, BMI and Waist Circumference (Randomized Safety Sample)
- CT-11.2 Incidence of Vital Signs of Potential Clinical Relevance (Randomized Safety Sample)
- CT-11.3.1 Listing of Vital Signs of Potentially Clinical Relevance by Subject(Safety Sample)
- CT-11.3.2 Criteria for Potentially Clinically Relevant Vital Sign Abnormalities
- CT-12.1 ECG Parameters - Mean Change from Baseline (Randomized Safety Sample)
- CT-12.2 Incidence of ECG Measurements of Potential Clinical Relevance (Randomized Safety Sample)
- CT-12.3.1 Listing of ECG Measurements of Potentially Clinical Relevance (Safety Sample)
- CT-12.3.2 Criteria for ECG Measurements of Potentially Clinical Relevance
- CT-13.1.1 Simpson-Angus Scale Total Score - Mean Change from Baseline by Week - OC (Open-Label Safety Sample)
- CT-13.1.2 Barnes Akathisia Rating Scale Global Score - Mean Change from Baseline by Week - OC (Open-Label Safety Sample)
- CT-13.1.3 AIMS Movement Rating Score - Mean Change from Baseline by Week - OC (Open-Label Safety Sample)
- CT-13.2.1 Columbia-Suicide Severity Rating Scale (C-SSRS) (children's version) - Suicidality (Open-Label Safety Sample)

- CT-13.2.2 Columbia-Suicide Severity Rating Scale (C-SSRS) (children's version) by Type (Open-Label Safety Sample)
- CT-14 Extent of Exposure to Investigational Medicinal Products in Open-Label Stabilization Phase (Open-Label Safety Sample)
- CT-15.1 Adverse Events (All Causalities) (Open-Label Safety Sample)
- CT-15.2.1 Incidence and Occurrence of Treatment-Emergent Adverse Events by System Organ Class and MedDRA Preferred Term (Open-Label Safety Sample)
- CT-15.2.2 Incidence of Treatment-Emergent Adverse Events by System Organ Class, MedDRA Preferred Term and Severity (Open-Label Safety Sample)
- CT-15.3.1 Incidence and Occurrence (Number of Events) of Potentially Drug-Related Treatment-Emergent Adverse Events by System Organ Class and MedDRA Preferred (Open-Label Safety Sample)
- CT-15.3.2 Incidence of Potentially Drug-Related Treatment-Emergent Adverse Events by System Organ Class, MedDRA Preferred Term and Severity (Open-Label Safety Sample)
- CT-15.4 Incidence of Deaths Due to Treatment-Emergent Adverse Events by System Organ Class and MedDRA Preferred Term (Open-Label Safety Sample)
- CT-15.5.1 Incidence and Occurrence (Number of Events) of Serious Treatment-Emergent Adverse Events by System Organ Class and MedDRA Preferred Term (Open-Label Safety Sample)
- CT-15.5.2 Incidence of Serious Treatment-Emergent Adverse Events by System Organ Class, MedDRA Preferred Term and Severity (Open-Label Safety Sample)
- CT-15.6.1 Incidence of Treatment-Emergent Adverse Events Resulting in Discontinuation from Trial by System Organ Class and MedDRA Preferred Term (Open-Label Safety Sample)
- CT-15.6.2 Incidence of Treatment-Emergent Adverse Events Resulting in Discontinuation from Trial by System Organ Class, MedDRA Preferred Term and Severity (Open-Label Safety Sample)
- CT-15.7 Incidence and Occurrence (Number of Events) of Non-Serious Treatment-Emergent Adverse Events by System Organ Class and MedDRA Preferred Term (Open-Label Safety Sample)
- CT-16.1.1 Laboratory Test Results for Serum Chemistry - Mean Change from Baseline (Open-Label Safety Sample)
- CT-16.1.2 Laboratory Test Results for Hematology - Mean Change from Baseline (Open-Label Safety Sample)
- CT-16.1.3 Laboratory Test Results for Urinalysis - Mean Change from Baseline (Open-Label Safety Sample)
- CT-16.1.4 Laboratory Test Results for Other Clinical Laboratory Tests - Mean Change from Baseline (Open-Label Safety Sample)
- CT-16.2 Incidence of Laboratory Values of Potential Clinical Relevance (Open-Label Safety Sample)
- CT-17.1.1 Vital Sign Parameters - Mean Change from Baseline (Open-Label Safety Sample)
- CT-17.1.2 Mean Change from Baseline in Weight, Height, BMI and Waist Circumference (Open-Label Safety Sample)
- CT-17.2 Incidence of Vital Signs of Potential Clinical Relevance (Open-Label Safety Sample)
- CT-18.1 ECG Parameters - Mean Change from Baseline (Open-Label Safety Sample)
- CT-18.2 Incidence of ECG Measurements of Potential Clinical Relevance (Open-Label Safety Sample)

- DREAS-1 Discontinued Subjects and Reasons for Discontinuation
- DREAS-2 Adverse Events for Subjects Who Discontinued from Trial due to Withdrew Consent
- PDEV-1 Protocol Deviations by Phase and Type of Deviation (Enrolled Sample)
- PDEV-2 Protocol Deviations by Phase, Country, Center and Type of Deviation (Enrolled Sample)
- PDEV-3 All Protocol Deviations by Subject
- PDEV-4 Protocol Deviations Criteria
- DEMOG-1 Demographic Characteristics
- SMED-1.1 Summary of Trial Medication Compliance in Double-Blind Randomized Withdrawal Phase (Randomized Sample)
- SMED-1.2 Trial Medication Compliance in Double-Blind Randomized Withdrawal Phase (Randomized Sample)
- SMED-2.1 Summary of Trial Medication Compliance in Open-Label Stabilization Phase (Enrolled Sample)
- SMED-2.2 Trial Medication Compliance in Open-Label Stabilization Phase (Enrolled Sample)

Protocol 31-14-204

EFF-1 Relapse Data

EFF-2.1 Yale Global Tic Severity Scale - Total Tic Score (YGTSS - TTS) and Total Yale Global Tic Severity Scale Score

EFF-2.2 Clinical Global Impressions Scale for Tourette's Syndrome (CGI-TS) Severity and Improvement Scores

AE-1.1 Adverse Events in Open-Label Stabilization Phase (Enrolled Sample)

AE-1.2 Adverse Events in Double-Blind Randomized Withdrawal Phase (Randomized Sample)

AE-1.3 Adverse Events in Follow-up Period (Enrolled Sample)

LAB-1 Laboratory Test Results: Serum Chemistry

LAB-2 Laboratory Test Results: Hematology

LAB-3 Laboratory Test Results: Urinalysis

LAB-4 Laboratory Test Results: Other Laboratory Tests

LAB-5 Laboratory Test Results: Urine Drug Screen

LAB-6 Laboratory Test Results: Urine Pregnancy Test (Enrolled Sample)

Proposed Patient Data Listings

PDATA-1 Consents and Eligibility

PDATA-2 Randomization List

PDATA-3.1 Subject Disposition

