3.7.3.5 Other Safety Assessments

3.7.3.5.1 Extrapyramidal Symptoms

3.7.3.5.1.1 Simpson-Angus Scale

The SAS¹⁶ consists of a list of 10 symptoms of parkinsonism (gait, arm dropping, shoulder shaking, elbow rigidity, wrist rigidity, head rotation, glabella tap, tremor, salivation, and akathisia). Each item will be rated on a 5-point scale, with a score of 1 representing absence of symptoms, and a score of 5 representing a severe condition. The SAS Total Score is the sum of the scores for all 10 items.

Protocol 31-14-204

3.7.3.5.1.2 Abnormal Involuntary Movement Scale

The AIMS¹⁴ assessment consists of 10 items describing symptoms of dyskinesia. Facial and oral movements (items 1 through 4), extremity movements (items 5 and 6), and trunk movements (item 7) will be observed unobtrusively while the subject is at rest (eg, in the waiting room), and the investigator will also make global judgments on the subject's dyskinesias (items 8 through 10). Each item will be rated on a 5-point scale, with a score of 0 representing absence of symptoms (for item 10, no awareness), and a score of 4 indicating a severe condition (for item 10, awareness/severe distress). For this scale, the subject is to be sitting on a hard, firm chair. In addition, the AIMS includes 2 yes/no questions that address the subject's dental status.

The AIMS Movement Rating Score is defined as the sum of items 1 through 7 (ie, items 1 through 4, facial and oral movements; items 5 through 6, extremity movements; and item 7, trunk movements).

3.7.3.5.1.3 Barnes Akathisia Rating Scale

The BARS¹⁷ consists of 4 items related to akathisia: objective observation of akathisia by the investigator, subjective feelings of restlessness by the subject, subject distress due to akathisia, and global evaluation of akathisia. The first 3 items will be rated on a 4-point scale, with a score of 0 representing absence of symptoms and a score of 3 representing a severe condition. The global clinical evaluation will be made on a 6-point scale, with 0 representing absence of symptoms and a score of 5 representing severe akathisia. To complete this scale, subjects will be observed while they are seated and then standing for a minimum of 2 minutes in each position. Symptoms observed in other situations (eg, while engaged in neutral conversation or engaged in activity on the ward) may also be rated. Subjective phenomena are to be elicited by direct questioning.

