7.6.5 Other Safety Data

7.6.5.1 Extrapyramidal Symptoms

Extrapyramidal Symptom scales including SAS, AIMS, and BARS scores will be evaluated by descriptively summarizing their changes from appropriate baseline for the Open-label Safety Sample and by treatment group for the Randomized Safety Sample. Results will be presented by visit.

Protocol 31-14-204

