9.3 Clinical Laboratory Data

Clinical laboratory tests include serum chemistry analysis, hematology analysis, urinalyses and other lab analysis. The potentially clinically relevant laboratory test abnormalities are listed by subject and by test for the safety samples. Criteria for identifying laboratory values of the potential clinical relevance are provided in [Appendix 1](#). Subjects with AST or ALT > 3 times upper limit of normal (ULN) value and total

bilirubin > 2 times ULN values if pre-treatment value is \leq ULN value, or with AST or ALT > 3 times pre-treatment value and total bilirubin > 2 times pre-treatment value if pre-treatment value is > ULN value, are listed by phase. The incidences of potentially clinically relevant laboratory tests abnormalities based on the observation from the scheduled and the unscheduled post-baseline visits will be tabulated for the safety samples. Descriptive statistics for the clinical laboratory measurements and changes from baseline at each scheduled trial week and last visit will be presented for the safety samples.

If laboratory tests assessments are repeated for the same visit, the last repeated values are used for summary tables. This is accomplished by sorting patient data by visit date and visit time (if applicable) within the same visit identification. If the lab data are recorded as ranges (i.e., including < or > limit of quantification), these data are not included in the calculations for changes from baseline but included in the calculations for incidences.

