9.4 Vital Sign Data

Vital signs include body temperature, heart rate, systolic blood pressure and diastolic blood pressure in supine and sitting position. In addition, body weight and waist circumference are measured. Potentially clinically relevant vital sign abnormalities will be listed by subject. Criteria for identifying vital signs of the potential clinical relevance are provided in [Appendix 2](#). Incidences of clinically relevant vital signs abnormalities based on the observation from the scheduled and unscheduled post-baseline visits will be tabulated safety samples. In addition to weight, BMI and waist circumference, vitals sign parameters at each trial week, and change from baseline at the post-baseline trial weeks will be summarized using descriptive statistics for the safety samples in the corresponding phases.

If vital sign assessments are repeated for the same trial week, the last repeat values will be used for production of mean change from baseline. This is accomplished by sorting patient data by visit date and visit time (if applicable) within the same visit identification.

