9.5 Electrocardiogram Data

All ECG analyses are made using observed data. Baseline is defined as average of ECG measurements at baseline visit as specified in [Section 5.2](#). Last visit for each phase is defined as average of ECG measurements at last visit as specified in [Section 5.2](#). Missing ECG data will not be imputed. For the calculation of QT correction by heart rate, QTc is missing only if all three consecutive beats are unreadable. If there is at least 1 beat available in the lead, the data are included in the analysis. For each ECG, QT and RR

intervals from three consecutive complexes (representing three consecutive heart beats) are measured manually. The QT correction is performed on beat-to-beat basis. The mean of ratios (beat-to-beat) is calculated by $(QT_{c1} + QT_{c2} + QT_{c3})/3$ using each QT-RR pair: (QT1, RR1), (QT2, RR2) and (QT3, RR3). The corrected QT intervals for QT_{cB}, QT_{cF}, and QT_{cN} are defined as follows:

- QT_{cB} is the length of the QT interval corrected for heart rate by Bazett's formula: $QT_{cB} = QT / (RR)^{1/2}$.
- QT_{cF} is the length of the QT interval corrected for heart rate by Fredericia's formula: $QT_{cF} = QT / (RR)^{1/3}$.
- QT_{cN} is the length of the QT interval corrected for heart rate by the FDA Neuropharm Division formula: $QT_{cN} = QT/(RR)^{0.37}$.

Potentially clinically relevant ECG abnormalities will be listed by subject. Criteria for identifying ECG measurements of the potentially clinically relevance are provided in [Appendix 3](#). The incidences of abnormal ECGs of potential clinical relevance based on the observation at the scheduled and the unscheduled post-baseline visits will be tabulated the safety samples. Descriptive statistics of change from baseline in ECG intervals of PR, QRS, RR, QT, QT_{cB}, QT_{cF}, and QT_{cN} will be presented at each scheduled trial week and last visit for the safety samples.

In summarizing the incidence of abnormalities, a patient must have had an evaluation that meets abnormality criteria by the end of trial phase. Incidence rate is calculated as the number of patients having at least 1 abnormality within the corresponding study phase divided by the number of patients who are both exposed to study medication and have an on-treatment evaluation within the same study phase.

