9.6 Other Safety Data

9.6.1 Extrapyramidal Symptoms

EPS rating scales include the Simpson-Angus Scale (SAS), Barnes Akathisia Rating Scale (BARS) and Abnormal Involuntary Movement Scale (AIMS). The following variables will be analyzed: 1) Change from Baseline in SAS Total Score, 2) Change from Baseline in BARS Global Score, 3) Change from Baseline in AIMS Movement Rating Score (i.e., total of item 1 to 7).

The SAS total score (range 10-50) is the sum of the rating scores for 10 items from the SAS panel in the eCRF. The BARS global score (range 0-5) is derived from the global

clinical assessment of akathisia from the BARS panel in the eCRF. The AIMS movement rating score (range 0-28) is the sum of the rating scores for facial and oral moments (i.e., item 1 - 4), extremity movements (i.e. item 5 - 6), and trunk movements (i.e. item 7) from the AIMS panel in the eCRF. A missing value of any item for SAS and AIMS movements scale could result in a missing SAS total score or AIMS movement rating score.

Changes from baseline in EPS scale scores will be summarized by trial week for the safety samples. EPS rating scale scores will be presented for OC datasets.

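### The three extrapyramidal scales are summarised only as change from baseline by week, so the scale tables do not show how many children per arm worsened at any time in a phase

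*SAP*

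**What the plan says.** SAP 9.6.1 names three variables: change in SAS total, in BARS global score and in AIMS movement rating score. It then gives the only reporting rule: "Changes from baseline in EPS scale scores will be summarized by trial week for the safety samples", on observed cases. Protocol 7.6.5.1 agrees: the scales "will be evaluated by descriptively summarizing their changes from appropriate baseline", with results by visit.

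SAP Appendix 4 lists six tables for these scales, CT-6.1.1 to CT-6.1.3 for the double-blind phase and CT-13.1.1 to CT-13.1.3 for the open-label phase. The BARS pair reads "CT-6.1.2 Barnes Akathisia Rating Scale Global Score - Mean Change from Baseline by Week - OC (Randomized Safety Sample") and "CT-13.1.2 Barnes Akathisia Rating Scale Global Score - Mean Change from Baseline by Week - OC (Open-Label Safety Sample"). The SAS and AIMS titles have the same form.

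Other safety domains also get a count of children:

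- Laboratory, SAP 9.3: "The incidences of potentially clinically relevant laboratory tests abnormalities" are tabulated against Appendix 1.
- Vital signs, SAP 9.4: "Incidences of clinically relevant vital signs abnormalities" are tabulated against Appendix 2.
- ECG, SAP 9.5: "The incidences of abnormal ECGs of potential clinical relevance" are tabulated against Appendix 3.
- Suicidality, SAP 9.6.2: incidence, emergence and worsening are each defined.

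**The concern.** SAS, BARS and AIMS are named safety endpoints in Protocol 3.5.2 and SAP 6.4. Each is an ordinal rating with a floor that means no symptoms. For BARS, "The global clinical evaluation will be made on a 6-point scale, with 0 representing absence of symptoms". When most children sit at or near the floor, the question of interest is how many moved away from it and how far. A weekly mean does not answer that: it gives the same value for a few marked cases and for many slight ones, and it offsets worsening against improvement.

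The week-by-week layout adds to this. Double-blind ratings are scheduled at Weeks 1, 4 and 12 or early termination (Protocol Table 3.7-2). In the open-label phase they are at Week 8 and at end of phase, which can fall at Week 14, 16, 18 or 20 depending on when the child is randomized (Protocol Table 3.7-1 and its notes). The end-of-phase ratings of randomized children can therefore be spread over up to four rows. SAP 9.3 and 9.5 add a last-visit summary for laboratory and ECG data, but SAP 9.6.1 does not. SAP 3.4 also keeps only the last value in a week window for summary tables, so a worse earlier unscheduled rating in that window would drop out.

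**Working it through.** **Score ranges.** The SAP's ranges can be rebuilt from the item descriptions in Protocol 3.7.3.5.1.

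- SAS: 10 items scored 1 to 5, so 10 × 1 = 10 to 10 × 5 = 50.
- AIMS movement rating: 7 items scored 0 to 4, so 0 to 7 × 4 = 28.
- BARS global: one 6-point item, 0 to 5.

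All three match SAP 9.6.1.

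**Inputs.** n = 38 per arm and 228 open-label are the planned sizes (Protocol 7.1, SAP 4). The documents give no rate or size of worsening, so k (children affected) and d (points of change) below are assumptions.

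**Formula.** If k children change by d and the rest do not change, mean change = k × d / n, while the share affected is k / n.

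| Scale and group | k | d | Mean change | Share affected |
|---|---|---|---|---|
| BARS, n = 38 | 3 | +3 | 9/38 = 0.24 | 3/38 = 7.9% |
| BARS, n = 38 | 9 | +1 | 9/38 = 0.24 | 9/38 = 23.7% |
| SAS, n = 38 | 2 | +10 | 20/38 = 0.53 | 2/38 = 5.3% |
| AIMS, n = 38 | 2 | +8 | 16/38 = 0.42 | 2/38 = 5.3% |
| BARS, n = 228 | 5 | +4 | 20/228 = 0.09 | 5/228 = 2.2% |

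The first two rows have the same mean for any arm size, because both numerators are 9. A smaller arm raises both means equally and does not separate them.

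**Offsetting.** Three children at +3 and nine at −1 give (3 × 3 − 9 × 1)/38 = 0. This needs nine children rated above 0 at the start of the phase. That is conceivable only at the double-blind baseline, which is taken on aripiprazole, and the documents give no such rate. It shows what can happen, not what is expected.

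**Spread.** With n = 38, the SD is 0.82 (maximum 3) for three children at +3, and 0.43 (maximum 1) for nine at +1. In the offset case it is 0.99, with a range of −1 to +3. The scenarios are therefore alike in the mean but not in the SD or maximum.

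**Link to adverse events.** Protocol 5.1 says when a laboratory value becomes an adverse event, and Protocol 3.7.3.3.1 does so for a new finding at the post-treatment physical examination. Neither document has such a rule for a SAS, BARS or AIMS score. Protocol 5.2 elicits adverse events by an open, non-leading question.

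**The case against.** The strongest answer is that affected children are already counted elsewhere. Akathisia, parkinsonism or dyskinesia reported as an adverse event appears per child, cumulatively over the phase, by preferred term and severity (CT-8.2.1, CT-8.2.2, CT-15.2.1, CT-15.2.2). It also appears in the discontinuation tables where relevant and in the by-phase adverse event listings. This stands. A reader might infer that such children vanish from the report, and the documents do not support that. The gap is limited to scale worsening that no one records as an adverse event.

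Second, a table titled by its mean may print more. SAP section 9 speaks of descriptive statistics, and where SAP 7.2 spells them out for demographics they include SD, minimum and maximum. If these are printed, the example cases can be told apart. A reader might infer that the tables cannot reveal marked cases at all; that goes too far. But the SAP does not say what the EPS tables print, and a maximum shows one extreme value, not a number of children.

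Third, by-subject EPS listings may exist: the patient data listings in Appendix 4 are not complete in the available text, so their absence cannot be alleged. A listing still gives no count by arm.

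Fourth, the SAP follows the protocol here, so there is no contradiction. The laboratory and vital-sign criteria are largely attributed to an FDA draft, whereas the cut-offs suggested below have no source in the documents. With few ratings per phase, the loss from having no worst-value summary may be small. These points limit the weight of the comment but do not remove it.

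Finally, SAP 8.1.1 states that the trial ended early, so 38 and 228 are planned sizes and the means may be less diluted than shown.

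**Conclusion.** The point holds in a limited form. For SAS, BARS and AIMS the plan gives change from baseline by week and nothing else by arm. It has no worst post-baseline value, shift or number worsening at any time, although the other objective safety domains and the C-SSRS have a per-child summary. Because no rule links a scale score to an adverse event, the TEAE tables do not fully substitute for the scale result.

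The size can only be illustrated: a BARS mean change of 0.24 in an arm of 38 is compatible with 3 children worsening by three points or 9 worsening by one. This rests on assumed counts, the planned arm size, and all other children being unchanged. It is a reporting gap in a named safety endpoint, best labelled a cheap improvement.

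**What to change.** Keep the six mean-change tables. Add the following to SAP 9.6.1 and Appendix 4, for the open-label phase and for each double-blind arm:

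1. A shift table of BARS global category, phase baseline against worst post-baseline. Worst should be taken over all ratings in the phase, including early termination and unscheduled ones, and not after the last-in-window selection of SAP 3.4.
2. Number and percentage of children worsening by at least 1 and by at least 2 points on BARS global, on any AIMS item 1 to 7, and on any SAS item. State the denominator as children with a phase baseline and at least one later rating.

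The baseline column of the shift table also shows symptoms already present on aripiprazole at randomization, which a change score records as zero.

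The cost is two or three extra tables per phase, with no new data. The planned analyses are already descriptive, so no error rate or power is affected. The downside is that the 1-point row will count ordinary one-point rater fluctuation, which is why the 2-point row should stand beside it.
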